## 5.5.6 Blood sample collection and plasma extraction for biobanking

Blood will be collected via venous puncture into 16ml serum, 6ml EDTA and 4ml sodium citrate vacutainers and centrifuged within 30 min of collection. Plasma should be transferred into Eppendorf tubes and stored at -80°C locally. In regular intervals these samples will be shipped on dry ice to the Biobank of the Medical University of Graz, where they will be stored at -80°C for future biomarker analyses. NT-proBNP and blood ketone bodies will be measured in batches from these stored biomarker samples.

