### 1.3 What do we need for analysis?

Every file must include – if the quality is sufficient – loops and images of the (1-3) parasternal long axis including M-mode of the dimensions of the left ventricle and M-mode of the dimensions of the aorta/left atrium; (4, 5) parasternal short axis on the level of the papillary muscle and on the level of the apex; (6-12) apical 4-chamber view with and without colour Doppler including one image with pulsed wave Doppler at the leaflets of the opened mitral valve and tissue Doppler on the medial mitral annulus and continuous wave Doppler at the origin of a tricuspid regurgitation (gradient over tricuspid valve); (13, 14) native apical 2-chamber view; (15) native apical 3-chamber view; and (16, 17) one loop of the apical 5-chamber view with colour Doppler and one image with the continuous wave Doppler in the aortic outflow tract. ECG leads should be connected to the echocardiography machine and ecg tracings should be recorded on each loop or image.

[figure not shown]
Protocol No: Version 2.17 Date: 17 October 2022

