5.3.2 Covariates adjustment

All analyses, including the primary analysis, will be adjusted for the variables used when stratifying the randomization. These variables are Sex and T2DM status. We will not be able to adjust for the variable centre as this might introduce too many categories. Analysis will also be adjusted for baseline levels of the dependent variables.

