7.1 Primary Efficacy Analysis

The primary efficacy endpoint is the change in NT-proBNP from baseline to week 26. This primary endpoint will be analysed on the ITT population using a linear mixed effect model (LMEM) where the dependent variable is the NT-proBNP and the fixed effects are treatment, visit, treatment by visit interaction, the stratification factors Sex and T2DM and the level of NT-proBNP at baseline. The random effect component will include patients and unstructured covariance will be assumed for the within-subject errors. In case of non-convergence problems other covariance structures, such as compound symmetry, will be applied until the problem is resolved.

In this analysis, no missing data will be imputed. It will be handled by using the LMEM which assumes the data to be missing at random (MAR process). At week 26, estimates of mean values, the mean differences between the treatment groups and the associated 2-sided 95% confidence interval will be derived from the LMEM model through the use of estimated marginal means (or LS-means).

To claim superiority of Empagliflozin over Placebo, this primary efficacy analysis must show a statistically significant effect of treatment at an alpha level of 5% and two-sided test direction.

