7.2.2 Secondary Efficacy analysis II

To assess the sensitivity of the above primary efficacy analysis to the analysis population, we will conduct the same primary efficacy analysis as above but by using the Per protocol

Statistical Analysis Plan EMMY trial

population instead of the ITT.

Secondary Efficacy analysis III

In this analysis, we use the absolute change in NT-proBNP from baseline to week 26 as the

primary endpoint. This endpoint will be analyzed on the ITT population, with no imputation

of missing values, and by using a multiple linear regression model where the dependent

variable is the absolute change in NT-proBNP and the independent variables are treatment,

Sex, T2DM and baseline level of NT-proBNP.

Secondary Efficacy analysis IV 7.2.4

In this analysis, we use the percent change in NT-proBNP from baseline to week 26 as the

primary endpoint. This endpoint will be analyzed on the ITT population, with no imputation

of missing values, and by using a multiple linear regression model where the dependent

variable is the percent change in NT-proBNP and the independent variables are treatment, Sex,

T2DM and baseline level of NT-proBNP.

Analyses of Secondary Endpoints

The change from randomization to week 26 of all continuous secondary endpoints will be

analysed in the same way as the primary efficacy endpoint as follows:

Analysis population: ITT

Missing data: no imputation to be performed. Missing data will be implicitly handled by using

the LMEM which assumes the data to be missing at random (MAR process).

Statistical model: LMEM with unstructured covariance matrix. At week 26, estimates of mean

values, the mean differences between the treatment groups and the associated 2-sided 95%

confidence interval will be derived from the LMEM model through the use of Least square

means (LS-means).

Safety Analyses

The safety section of the analysis will contain a descriptive listing of the following tables:

All-Cause Mortality: A table of all cases of deaths due to any cause, with number and frequency

of such events in each arm/group of the clinical study.

Serious Adverse Events: A table of all anticipated and unanticipated serious adverse events, grouped by organ system, with number and frequency of such events in each arm/group of the clinical study.

This table will also include the reporting of cases of diabetic ketoacidosis.

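### The planned mixed model does not cover a missing baseline, so followed-up patients drop out of the echo and ketone analyses by default

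*SAP*

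**What the plan says.** **Model.** The primary model in SAP 7.1 has fixed effects for treatment, visit, their interaction, and "the stratification factors Sex and T2DM and the level of NT-proBNP at baseline". SAP 5.3.2 extends this to all analyses: "Analysis will also be adjusted for baseline levels of the dependent variables".

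**Missing data.** For the primary analysis, SAP 7.1 says that "no missing data will be imputed. It will be handled by using the LMEM which assumes the data to be missing at random". Under Analyses of Secondary Endpoints, the continuous secondary endpoints are to be "analysed in the same way as the primary efficacy endpoint as follows": ITT population, the same type of model with unstructured covariance, and "Missing data: no imputation to be performed. Missing data will be implicitly handled by using" the mixed model, again under MAR.

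**Population.** SAP 5.2.1 defines ITT as randomised plus at least one dose. A baseline value is not required.

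**Safeguards.** SAP 8.3 accepts a local NT-proBNP value when the central one is not available. SAP 7.2.1 repeats the primary analysis after multiple imputation at all visits. SAP 7.2 ties these sensitivity analyses to the primary endpoint.

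**Data sources.** On echo, Appendix C 1.3 of the protocol says "Every file must include – if the quality is sufficient", followed by the required views. On ketones, protocol 5.5.6 says "NT-proBNP and blood ketone bodies will be measured in batches from these stored biomarker samples"; Table 2 of the protocol lists no ketone test.

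**The concern.** The likelihood of a mixed model conditions on its covariates. Under MAR it uses whatever responses a patient has, but a patient whose baseline covariate is missing has no usable row at any visit. The SAP neither names this case nor gives a rule for it, and its text reads as though the mixed model had dealt with missing data.

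Two things are at stake. The analysed set can be smaller than the ITT set that the SAP names, and week-26 measurements already collected would go unused. The exposure is greatest where no fallback exists. Ejection fraction, diastolic function and beta-hydroxybutyrate, each at weeks 6 and 26, make up 6 of the 13 secondary endpoints in SAP 2.2.2.

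**Working it through.** **1. The plan's own figure.** Appendix A gives a baseline mean of 653.66, a 6-month mean of 282.66, SDs of 772.98 and 289.60, r = 0.85, a relative reduction of 0.4, two-sided 5% alpha and 80% power.

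- Variance ratio m = (289.60/772.98)² = 0.1404.
- SD of change = √(1 + m − 2r√m) × 772.98 = 548.46.
- Δ = 0.4 × (653.67 − 282.67) = 148.4.
- n per arm = 2(1.960 + 0.842)² × 548.46² / 148.4², which rounds up to 215. The plan states 216, so the figure reproduces.
- 216 × 1.10 = 237.6, giving the stated 238 per arm and 476 in total. The 10% is described as dropout; missing baselines are not mentioned.

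**2. Does the model drop these patients?** I simulated 476 patients with complete follow-up at three visits, of whom 83 had no baseline, and fitted a mixed model with baseline as a covariate.

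- Patients kept: 476 − 83 = 393.
- Rows kept: 1428 − 83 × 3 = 1179.
- All 249 follow-up values of the 83 patients were lost.

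**3. What keeping them would gain.** The share f without a baseline is not in the documents and is assumed. At f = 5%, 10% or 20%, about 24, 48 or 95 of 476 patients are affected. The correlation r is 0.85 in the NT-proBNP sample-size section; none is given for echo or ketones, so 0.5 is shown as well. I assume unit variance, the same r between all visits (compound symmetry) and complete follow-up.

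- Baseline as covariate, with deletion: SE² = 4(1 − r²) / [476(1 − f)].
- Baseline as a response with a common mean: the information matrix is the sum over arms of 238 × [(1 − f) X′V⁻¹X + f X₊′V₊⁻¹X₊], where the subscript + leaves out the baseline row. The SE of the week-26 contrast comes from its inverse.
- Gain in effective sample size = (SE with deletion / SE with common mean)² − 1.

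Echo and biobank samples have two follow-up visits (weeks 6 and 26). NT-proBNP has three (weeks 6, 12 and 26).

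| r | f | SE, deletion | SE, common mean (2 / 3 visits) | Gain (2 / 3 visits) |
|---|---|---|---|---|
| 0.50 | 0 | 0.0794 | 0.0794 / 0.0794 | 0 / 0 |
| 0.50 | 10% | 0.0837 | 0.0803 / 0.0802 | 8.6% / 8.8% |
| 0.50 | 20% | 0.0888 | 0.0813 / 0.0812 | 19.3% / 19.6% |
| 0.85 | 0 | 0.0483 | 0.0483 / 0.0483 | 0 / 0 |
| 0.85 | 10% | 0.0509 | 0.0498 / 0.0496 | 4.6% / 5.2% |
| 0.85 | 20% | 0.0540 | 0.0514 / 0.0512 | 10.1% / 11.4% |

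With no missing baselines the two models have the same SE. With a single follow-up visit the gain would be [(1 − f) + f(1 − r²)]/(1 − f) − 1. At r = 0.85 that is only 3.1% (f = 10%) and 6.9% (f = 20%), because there is no other follow-up visit to stand in for the missing baseline.

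**The case against.** **The primary endpoint is protected.** This largely stands. NT-proBNP is drawn and measured locally at Visit 1, so its baseline is lost only if both the central and the local value fail. The no-imputation rule in SAP 7.1 covers that analysis alone, and the imputation in SAP 7.2.1 can fill a baseline. A reader might infer that the superiority claim is compromised; the documents do not support that. Superiority still rests on the unimputed model, so the protection is not complete.

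**No bias is shown.** This stands. A reader might infer that dropping patients biases the treatment comparison. Protocol 5.4 lists the Visit 1 echo and biobank sample before randomisation, so whether they are missing should not depend on arm.

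**The concentration in echo and ketones is inferred.** This also stands. No missing-baseline count is given, and the image-quality condition applies to follow-up scans as much as to baseline. A reader might infer that acute-phase scans fail more often, but the documents do not say so. What they do show is that these endpoints have no fallback and no imputation analysis.

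**The SAP does not prescribe deletion.** True: deletion is the software default. But the SAP offers no other rule.

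**Simpler repairs may do.** A reader might infer that filling a missing baseline with the overall mean must be ruled out. That is not supported: in simulation with 10% missing it was more precise than deletion at r = 0.3, 0.5 and 0.7, and less precise only at 0.85.

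**Conclusion.** The point holds for the continuous secondary endpoints, chiefly ejection fraction, diastolic function and beta-hydroxybutyrate. As written, the missing-data statement is not true of a missing baseline, and the fitted models can leave out ITT patients who have follow-up data. For NT-proBNP the practical effect is probably small.

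The loss is in precision and in fidelity to ITT. Under the assumed missing rates, keeping these patients lowers the standard error by about 2% (r = 0.85, 10% missing) to 9% (r = 0.5, 20% missing). The mechanism is certain. The size rests on assumed missing rates and correlations, compound symmetry and complete follow-up. The documents give no power calculation for the echo or ketone endpoints, so no loss of power can be stated for them. The point is worth correcting but does not threaten the primary result.

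**What to change.** Under Analyses of Secondary Endpoints, and in SAP 7.1 for consistency, move baseline from the covariates into the response vector. Specify one common baseline mean for both arms, unstructured covariance over all visits including baseline, and the treatment contrast at week 26. The MAR statement then covers baseline too. With complete data the week-26 estimate is essentially that of the present model.

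For each model, report how many patients are analysed, by arm. SAP 6.1 plans its missing-data table for the primary endpoint only.

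The cost is SAP wording and a modest change of model code; no new data are needed. The planned subgroup analysis by baseline level (SAP 5.3.3) still needs an observed baseline, so its patient count should be given as well.

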7.2 Secondary Efficacy Analyses

To support the interpretation of the primary efficacy analysis, some robustness and/or sensitivity analyses will be performed on the primary efficacy endpoint. However, the conclusion of superiority for comparison of the primary endpoint between the two treatment groups is purely based on results of the primary efficacy analysis.

Secondary efficacy analyses will be performed to assess robustness of the results against missing data, analysis population, and the statistical model used.

7.2.1 Secondary Efficacy analysis I

To assess the sensitivity of the above primary efficacy analysis to missing data, analysis will also be conducted on the ITT population with missing values being imputed at all visits using the Multiple Imputation with Chained Equation (MICE) approach as described in section 5.4. Ten imputed data sets with all visit values filled in will be generated. The primary efficacy analysis described above will then be performed on each of the 10 imputed datasets, which will produce estimates of treatment effect and the standard error of that estimate. Finally, the set of estimates and standard errors will be analyzed by mice package to produce overall (pooled) estimates, confidence intervals, and P-values for the treatment effect.

7.2.2 Secondary Efficacy analysis II

To assess the sensitivity of the above primary efficacy analysis to the analysis population, we will conduct the same primary efficacy analysis as above but by using the Per protocol

Statistical Analysis Plan EMMY trial

population instead of the ITT.

Secondary Efficacy analysis III

In this analysis, we use the absolute change in NT-proBNP from baseline to week 26 as the

primary endpoint. This endpoint will be analyzed on the ITT population, with no imputation

of missing values, and by using a multiple linear regression model where the dependent

variable is the absolute change in NT-proBNP and the independent variables are treatment,

Sex, T2DM and baseline level of NT-proBNP.

Secondary Efficacy analysis IV 7.2.4

In this analysis, we use the percent change in NT-proBNP from baseline to week 26 as the

primary endpoint. This endpoint will be analyzed on the ITT population, with no imputation

of missing values, and by using a multiple linear regression model where the dependent

variable is the percent change in NT-proBNP and the independent variables are treatment, Sex,

T2DM and baseline level of NT-proBNP.

Analyses of Secondary Endpoints

The change from randomization to week 26 of all continuous secondary endpoints will be

analysed in the same way as the primary efficacy endpoint as follows:

Analysis population: ITT

Missing data: no imputation to be performed. Missing data will be implicitly handled by using

the LMEM which assumes the data to be missing at random (MAR process).

Statistical model: LMEM with unstructured covariance matrix. At week 26, estimates of mean

values, the mean differences between the treatment groups and the associated 2-sided 95%

confidence interval will be derived from the LMEM model through the use of Least square

means (LS-means).

Safety Analyses

The safety section of the analysis will contain a descriptive listing of the following tables:

All-Cause Mortality: A table of all cases of deaths due to any cause, with number and frequency

of such events in each arm/group of the clinical study.

Serious Adverse Events: A table of all anticipated and unanticipated serious adverse events, grouped by organ system, with number and frequency of such events in each arm/group of the clinical study.

This table will also include the reporting of cases of diabetic ketoacidosis.

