#### 5.6 Benefit-Risk Assessment

Empagliflozin has been studied in subjects with type 2 diabetes and demonstrated cardiovascular benefit in terms of reduction of a 3-point MACE composite endpoint as well as of hospitalization for heart failure. However, it has not been studied shortly after myocardial infarction yet. Given that the drug is not causing hypoglycemic events per se, hypoglycemia appears not to be a major issue in subjects without diabetes, that are studied in this trial as well. When

Protocol No: Version 2.17 Date: 17 October 2022

Empagliflozin is used together with sulfonylurea or insulin, hypoglycemia might occur and therefore participants will be instructed to reduce concomitant antihyperglycemic medication accordingly.

Fungal genital infections are the most common side effect of Empagliflozin and participants will be informed about this and instructed on prevention measures. Rarely, serious infections of the genitals and the area around the genitals have been reported. This infection, called necrotizing fasciitis of the perineum, is also referred to as Fournier's gangrene.

In people with type 2 diabetes mellitus, the risk for ketoacidosis is increased, in particular in situations such as insulin deficiency, alcohol abuse, exsiccosis or infections.

There will be no direct beneficial effect for all participants, however, those participants with known diabetes mellitus type 2 randomised to the Empagliflozin group will benefit from the glucose lowering effect of the drug.

Overall this trial aims to develop novel future strategies for heart failure prevention in subjects with acute myocardial infarction.

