2.1.3 Safety objectives

- All-cause mortality
- Number of serious adverse events
- Number of severe hypoglycaemic events (i.e. requiring third party assistance)
- Number of genital infections
- Number of ketoacidotic events
- Changes in liver function parameters (AST, ALT, GGT)
- Changes in renal function parameters (creatinine, eGFR)

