5.2.3 Safety Population

All patients who were randomized and received at least one confirmed dose of study medication (i.e. Empagliflozin or Placebo) and provided any post-baseline safety information.

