8.3 Clinical Laboratory Evaluations

Summary statistics on laboratory measurements will be tabulated. For baseline values, differences in normal ranges between sites will be provided.

The primary outcome, NTproBNP, is assessed at the central lab. If measurement in the central lab are not possible (e.g. missing biomarker sample), NTproBNP measurement from the local lab will be accepted for the analysis.

9 Reporting Conventions

P-values ≥0.001 will be reported to 2 significant figures; p-values less than 0.001 will be reported as "<0.001". The mean, standard deviation, and any other statistics other than quantiles, will be reported to one decimal place greater than the original data. Quantiles, such as median, or minimum and maximum will use the same number of decimal places as the original data.

EMMY trial

Statistical Analysis Plan

EMMY trial

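### SAP section 8 plans by-arm counts only for deaths, serious adverse events and diabetic ketoacidosis, so several named or defined safety events have no planned count unless they are serious

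*SAP*

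**What the plan says.** **Planned output.** SAP section 8 (Safety Analyses) opens: "The safety section of the analysis will contain a descriptive listing of the following tables". Two tables follow, each with number and frequency by arm. The first is all-cause deaths. The second is "Serious Adverse Events: A table of all anticipated and unanticipated serious adverse events, grouped by organ system, with number and frequency", to which one item is added: "This table will also include the reporting of cases of diabetic ketoacidosis". Section 8.1 (exposure) is unedited template text, and section 8.2 covers pregnancies. Section 8.3 says: "Summary statistics on laboratory measurements will be tabulated. For baseline values, differences in normal ranges between sites will be provided". SAP section 6 gives summary tables a column per treatment and defines the summary of a continuous variable as n, mean and standard deviation. The SAP plans no table of all adverse events, non-serious adverse events or adverse events of special interest (AESIs). Protocol 7.2 adds no safety analysis.

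**Objectives.** SAP 2.1.3 lists five items that are counts: deaths, SAEs, severe hypoglycaemic events (those needing help from a third party), "Number of genital infections", and ketoacidotic events. It also lists changes in liver and renal parameters.

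**Protocol background.** Section 5.6 states: "Fungal genital infections are the most common side effect of Empagliflozin". Section 6 has every adverse event recorded on the case report form. Section 6.5 singles out AESIs as a concern for safety assessment in this trial and names four groups: hepatic injury, decreased renal function, acidosis including ketoacidosis, and lower-limb amputation. The hepatic and renal groups are defined by thresholds that an individual patient either meets or does not.

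**Population.** SAP 5.2.3 defines a safety population, which begins: "All patients who were randomized and received at least one confirmed dose of study medication".

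**The concern.** The objectives and the protocol's AESI definitions ask how many patients had certain events. The planned tables answer that only for deaths, events classed as serious, and diabetic ketoacidosis. A genital infection treated in outpatient care, or a doubling of creatinine found at a scheduled visit in a patient who stays well, appears in no by-arm table.

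At stake is the completeness of the safety report. It could meet SAP section 8 in full and still leave out the per-arm number of patients with the drug's commonest known side effect. It could also leave out how many crossed a renal or hepatic threshold that the protocol itself defined. If such counts are added later, the choice of events and thresholds could be made with the allocation known.

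**Working it through.** The point rests on no figure in the plan, so the check sets objectives and definitions against planned outputs.

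**Step 1: the five counts in SAP 2.1.3 against SAP section 8**

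| Objective | Planned by-arm count |
|---|---|
| All-cause mortality | Yes, own table |
| SAEs | Yes, own table |
| Ketoacidotic events | Partly: diabetic ketoacidosis is added to the SAE table; other ketoacidotic events appear only if serious |
| Severe hypoglycaemia | Partly: many cases will be SAEs, but inside an organ-system table with no dedicated row |
| Genital infections | Only if serious |

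So two are covered, two are partly covered, and one is missing except for serious cases. The ketoacidosis row matters because the trial enrols patients without diabetes, and AESI group 6.5.3 is wider than diabetic ketoacidosis.

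**Step 2: the four AESI groups in Protocol 6.5**

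- Hepatic (6.5.1): ALT and/or AST at least 5 times ULN alone, or at least 3 times ULN with total bilirubin at least 2 times ULN. Non-serious cases are not counted.
- Renal (6.5.2): creatinine at least twice baseline and above ULN. Non-serious cases are not counted.
- Acidosis (6.5.3): only diabetic ketoacidosis is certain to be counted.
- Amputation (6.5.4): the protocol puts these on an SAE report, so they reach the SAE table.

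**Step 3: can the laboratory summaries stand in for a count?** This is an illustration with assumed values: 238 per arm (the planned enrolment), baseline creatinine 1.0 mg/dL, SD of change 0.20 to 0.30 mg/dL, zero mean change otherwise, and creatinine doublings in 4 patients against 1.

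- Shift in the mean difference: 3 × 1.0 / 238 = 0.0126 mg/dL.
- Standard error of the difference: SD × √(2/238) = 0.0183 (SD 0.20) to 0.0275 (SD 0.30).
- Shift in standard errors: 0.0126/0.0183 = 0.69, down to 0.0126/0.0275 = 0.46.
- Arm SD with k doublings: √[((238−k)/238)·SD² + (k/238)(1−k/238)]. At SD 0.20 this gives 0.236 (k = 4) against 0.210 (k = 1). At SD 0.30 it gives 0.324 against 0.306.

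The SDs hint at a tail, but a reader cannot recover 4 and 1 from them.

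**Step 4: what a count would show.** Event numbers are again assumed, with 238 per arm and Newcombe 95% intervals.

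- Genital infections 10 v 2: 3.4 points (0.5 to 6.8).
- Genital infections 8 v 3: 2.1 points (−0.8 to 5.3).
- Renal threshold 4 v 1: 1.3 points (−0.9 to 3.8).

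With 216 per arm, 10 v 2 gives 3.7 (0.5 to 7.5) and 4 v 1 gives 1.4 (−1.0 to 4.2). Whether an interval excludes zero depends on the split assumed. These figures show only that such a table would be imprecise; they say nothing about the trial's results.

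**The case against.** **No objective asks for AESI counts.** This stands. Protocol 2.3 and SAP 2.1.3 word the renal and liver items as parameter changes, and the by-arm laboratory summaries serve those. A reader might infer that the plan fails its renal and hepatic objectives; the documents do not support that. The case for counting threshold crossers rests on Protocol 6.5, which defines them with safety assessment in mind, and on good practice.

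**Severe hypoglycaemia is largely captured.** This mostly stands. Protocol 6.6 says that important events which may jeopardise a subject, or need intervention to avert a serious outcome, should be treated as serious. An event needing third-party help will often qualify, although medical judgement still applies. What is missing is chiefly a dedicated row.

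**The tables named need not be the only ones.** A reader might infer that the trial will be unable to report these counts. That is too strong. SAP 2.1.3 shows the intent to count genital infections and severe hypoglycaemia, the data are on the case report forms, and section 8 does not say that nothing else may be produced. SAP section 6 also prescribes frequencies for categorical variables. But that rule says how to summarise a variable, and section 8 makes neither event type nor threshold crossing a variable to be tabulated. The intended counts were not carried into a planned output.

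**AESIs are reported to the manufacturer.** True, but expedited case reporting is not a comparison by arm.

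**Conclusion.** The point holds as a minor gap between objectives and planned output. As written, SAP section 8 yields no by-arm count of non-serious genital infections. It has no separate row for severe hypoglycaemia, no count of non-serious ketoacidotic events outside diabetic ketoacidosis, and no count of patients meeting the renal or hepatic AESI thresholds without a serious event. Genital infection is the clearest omission, being both a named count and the commonest known side effect.

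The conclusion rests on reading section 8 as the full list of planned event tables; nothing elsewhere in the SAP or Protocol 7.2 extends it. It does not depend on the assumed event numbers. The primary efficacy analysis is unaffected.

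**What to change.** Add to SAP section 8 one descriptive by-arm table in the safety population, giving patients n (%) for:

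- genital infections, serious or not;
- severe hypoglycaemia (third-party assistance);
- all ketoacidotic events;
- investigator-reported AESIs by type, serious or not;
- scheduled post-baseline creatinine at least twice baseline and above ULN;
- scheduled post-baseline ALT or AST at least 5 times local ULN.

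The AESI row also covers unscheduled samples and the combined bilirubin criterion, since total bilirubin is not among the scheduled tests in Protocol Table 2. Keep the laboratory mean and SD tables. Risk differences with confidence intervals, onset dates, and baseline AST and ALT alongside (the infarct itself can raise AST) are optional.

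The cost is SAP wording and one table. Adverse events are already recorded, and creatinine, ALT and AST are drawn at visits 1 to 4. Local ULNs must be available for post-baseline visits; that is assumed, because SAP 8.3 mentions normal ranges only for baseline. Draws at weeks 6, 12 and 26 can miss transient rises, which the AESI row covers in part. Events may be few, so the table should stay descriptive.
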